5.4 Statistics

5.4.1 Handling data with missing values

Our data analysis techniques are capable of dealing with data that are of heterogeneous nature, from multiple devices, modalities, and results of validated questionnaires that are neither normalised nor complete. The algorithms will identify reliable and robust patterns within the data that define shared, homogeneous, rule based categories with common "frailty signatures".

Missing values and measurement noise will be handled by data imputation where prediction is based on unsupervised clustering. We will apply reconstruction of missing parts by applying statistical models learned by available complete data. In particular, data missing from individual subjects and/or sources of information will be estimated based on state-ofthe-art techniques and building upon UoP's existing s/w tools. Missing parts will be reconstructed by applying models learned from available complete data borrowing ideas from subspace learning. The most homogeneous clusters with respect to frailty will be detected, and interpretable rules will be extracted from them. Also potential associations with features or categories of interest will be investigated.

In addition to clustering, similarity analysis will be performed. Wavelet and tensor-based decomposition for automatic summarization and concept discovery of high-order datasets by allowing reasoning across all modes of data concurrently (TWave and TWaveCluster) (85) will be used.

The heterogeneous sources of data will be fused either using tensor-based techniques or standard data-mining methods (e.g., kernels, decision trees).

A higher level of information fusion will be applied e.g., ensemble methods that boost the decisions made from different models on individual sources. In such scenarios, data missingness can be handled by emphasizing the importance of data objects with partial

information compared to the common ones. After integrating the heterogeneous data, knowledge discovery on the multidimensional spaces will be performed.

5.4.2 Soundness of conclusions – Sample calculations – Large number of parameters and many "micro" samples

Our main goal is to explore the relationships of the different parameters measured with the frailty of the older people. A risk appears since the number of parameters is large, the project's objectives numerous and the participant population limited. As the number of participants cannot be changed, the statistical methodology to be applied is intended to address the dimensionality problem by applying different dimensionality reduction techniques (e.g., step-wise forward feature selection, step-wise backward feature elimination, decision tree induction, principal component analysis,) as well as clustering techniques to partition the data into more homogeneous groups. For example grouping equivalent comorbidities is expected to improve the statistical significance leading to more sound conclusions regarding comorbidities and frailty.

Moreover, correlation analysis can provide us with information on the measure of correlation between two or more parameters. A common measure of correlation or linear relationship between two random variables is the covariance. Another measure of correlation between two random variables, which is often more interpretable is the Pearson correlation, which is an efficient (parametric) statistical indicator to assess whether there is a link between two variables and how to combine them and cluster them in equivalent ones. This way we can perform dimensionality reduction, more efficient exploitation of the clinical trial subject number and obtain increased statistical reliability of the result. The term parametric refers to a series of statistical indicators that meet specific conditions that may be empirical or even laboratory measurements. If these conditions are "missing", one can use non-parametric statistical indicators, which are not affected by compliance or the "violation" of conditions. For the Pearson correlation coefficient, these conditions are: variable representation should be continuous scale of equal intervals that are normally distributed and there is a linear relationship between the two variables to be combined. What is required for the detection of the relationship is to have a proportional relationship between the two variables at all levels. The bigger one can grow over the other one and vice versa. The scattering diagram is a very useful diagram which illustrates the type and (approximately), the size of relationship of the two variables to be clustered together.

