2.2 Participants' characteristics

The Clinical study will be performed in 3 Clinical Centers: University of Patras (UoP), Greece; INSERM-Nancy, France; and MATERIA- Nicosia, Cyprus. Each Center will recruit 170 individuals for the FrailSafe study. By this way a total of 510 community living subjects aged 70 years and older will be recruited. The inclusion and non-inclusion criteria are demonstrated in table 1.

Table 1. Inclusion and exclusion criteria

Inclusion criteria
Age ≥70 years
Informed consent provided
Exclusion criteria
Lack of wish to participate
Consent withheld
Inability to give consent because of incapacity
Inability to walk
Inability to speak Greek or French (see clinical centers)
Diagnosis of clinically significant cognitive impairment or score less than 24 on the Mini– Mental State Examination
Diagnosis of advanced malignancy, other terminal illness or an estimated life expectancy of less than 12 months
Active psychiatric disorder based on medical records or clinical opinion at the time of recruitment, current substance users, or excessive alcohol drinkers.

The numerical threshold for "older age" has always been controversial, though most widely accepted was the age of 65 years, corresponding in the usual age of retirement. Still, nowadays "young old" individuals maintain a good general health condition and with the exception of special cases, frailty is most likely to be encountered in older age ranges. In the FrailSafe study, since we need to include people in non-frail, pre-frail, as well as frail conditions, it was decided that the age threshold will be that of 70 years.

In order to be able to comply better with the requirements of the study (usage of technical material, cooperation for the testing of novel equipment, need for participant's feedback and relatively long follow up period), subjects with highly debilitating conditions, such as inability to walk, presence of clinically significant cognitive impairment, or active psychiatric

disorder will be excluded from the study. Similarly, subjects with serious medical conditions that convey a guarded prognosis (estimated life expectancy of less than 12 months) will be excluded as well.

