2.3 Groups

All participants will be given a unique number by the time they are allocated in four groups (table 2), with the addition of the code number of each centre in front: (1 for Patras, 2 for Cyprus and 3 for Nancy). For each centre, participants with numbers 001 to 080 will belong to the Start Up Group (A), the 40 following will belong to the Main Group (B), the 25 following afterwards will belong to the Evaluation Group (C) and the last 25 to the Control Group (D). The Evaluation Group (C) will be further divided in two parts: participants with numbers 121-140 will belong to the "standard" Evaluation Group; while those with numbers 141-145 will belong to the Long Term Evaluation Group, with an augmented intensity of following up.

Group	Serial Number
A- Start Up	001-080
B- Main	081-120
C- Evaluation	121-145
Ci- Standard Evaluation	121-140
Cii- Long term Evaluation	141-145
D- Control	146-170
With the prefix of the centre number	1 for Patras, Greece
	2 for Nicosia, Cyprus
	3 for Nancy, France

Table 2. Participants' ID numbers

In case of exclusion or premature withdrawal of a participant, (s)he has been replaced by a new subject, to whom a new unique ID number has been given. The substitute subjects were given the number of the individual they have replaced with the addition of 500. For example, if the participant number 1094 withdrew from the study (subject number 94 from the first recruitment centre), the subject that replaced him/her will take the number 1594

(=1094+500). For subject number 3164 who withdrew (participant number 164 from the third recruitment centre), the subject replacing him/her will take the number 3664 (=3164+500). However, participants' replacements took place only until M19. Any subject that dropped off after July 2017, has not been and will not be replaced due to lack of time for catching up with the minimum follow up time period required (M19 represents the middle timeline of the project).

The number of the participants allocated in each group is already agreed in the original proposal and corresponds mostly to issues of availability of material and workforce in the context of actual financial potential and less to pure mathematical calculations, due to the originality of the project and the absence of a previous reference to consider for sample size calculations.

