This stratification of frailty according to Fried's criteria will not be used in the analysis of data. The study population will be considered as a whole, from which new frailty metrics will be identified using both hard and proxy outcomes; the latter will be based on the change of clinical and FrailSafe parameters.

The sample in this study should ideally be randomly selected from the general population in those aged \geq 70 years. This would require a larger number of participants and a larger number of study workforce, as well as equipment, in order to include individuals with the right case mix of frailty levels and a representative number of comorbidities. Undoubtedly, such a design would have been preferred and would have provided strong and reliable clinical results. However, current financial resources in this Horizon 2020 call, which are split among technological development and clinical evaluation, were not sufficient for this type of methodology.

It is understandable that transition among the groups as defined by Fried's criteria might not be easily observed with the current study design, as number of participants, time span and number of simultaneous FrailSafe assessments are limited. On the other hand, functional changes or proxy outcomes expressing loss of functional reserve is likely to be detected when the study group is examined as a whole. The choice of the current clinical study methodology was a compromise between an ideal approach and a more practical solution, though hampered by numerous limitations.

In addition, in each of the three frailty status, at least 7 have prior stroke, 7 MCI (Mild Cognitive Impairment), 7 either osteoporosis for women or osteoarthritis for men and 7 nothing of the mentioned above. There is no particular concern in which group they will

belong. If this will not be achieved by randomization, the investigator, who will be in charge to overall monitor randomization, will intervene to further randomly stratify cases to obtain this pre-specified study objective.

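### Clustering is used both to fill in missing values and to find the frailty categories, so part of the clusters' apparent homogeneity can come from the imputation

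*Protocol*

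**What the plan says.** One paragraph of section 5.4.1 fixes both steps.

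- Imputation: "Missing values and measurement noise will be handled by data imputation where prediction is based on unsupervised clustering". It adds: "Missing parts will be reconstructed by applying models learned from available complete data borrowing ideas from subspace learning".
- Search: "The most homogeneous clusters with respect to frailty will be detected, and interpretable rules will be extracted from them".

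The section's stated aim is homogeneous, rule-based categories that share a frailty signature. Section 5.4.2 clusters again for dimension reduction: "as well as clustering techniques to partition the data into more homogeneous groups".

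On an outside yardstick for frailty, section 2.4 says of the Fried categories: "This stratification of frailty according to Fried's criteria will not be used in the analysis of data". Its next sentence says that new frailty metrics will be identified from the hard and proxy outcomes.

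Section 5.4.1 does not keep the two uses of clustering apart. It has no clustering of observed data only, no check of the clusters on held-out participants and no stability requirement. Giving more weight to partial records is mentioned, but only as a possibility in the later ensemble step.

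**The concern.** A value predicted from a cluster is pulled towards that cluster. When the completed data are clustered again, the same groups reappear with less spread inside them. Choosing the most homogeneous clusters then partly rewards the imputation. This needs no informative missingness, so it is separate from the question of who has missing data.

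Device data will clearly be incomplete. Section 3.7.8 lists the strap sensor for one participant at a time, while section 2.6 allows up to five simultaneous sessions. Section 2.5 gives the control group no device at all, which is 25/170 = 14.7% of each centre. At stake is whether rules presented as frailty signatures describe older people or describe gaps in the recordings, with more gaps giving a sharper picture.

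**Working it through.** The protocol states no figure on this point, so there is none to reproduce. The mechanism is shown first by algebra and then by simulation.

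**Inputs from the protocol.** Groups A and B hold 3 × (80 + 40) = 360 people (section 2.3). The order of imputation and search is that of section 5.4.1.

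**Assumptions not in the protocol.** Missing rate, number of clusters k, number of variables, correlation between variables, missingness completely at random, and the exact filling rule.

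**Algebra.** Let B and W be the between-cluster and within-cluster sums of squares among observed cells, scaled so that B + W = 1, and let m be the missing fraction. Filling at the cluster mean adds nothing to W. The between-cluster share in the completed data is therefore about

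B / (B + (1 − m)W).

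In one run with independent variables, the observed-cell share was 10.3% at 20% missing and 15.5% at 50%.

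- m = 0.2: 0.103 / (0.103 + 0.8 × 0.897) = 0.126. Simulated: 12.4%.
- m = 0.5: 0.155 / (0.155 + 0.5 × 0.845) = 0.268. Simulated: 26.2%.

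With no missing data the same run gave 8.3%. So the observed cells are themselves raised (10.3 to 15.5% against 8.3%), because the labels are fitted to fewer cells. A check on observed cells of the same participants is not enough.

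**Simulation 1.** 360 people, 20 variables with no true clusters, k = 3, iterated cluster-mean filling, 12 data sets per setting. Independent variables:

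| Missing | Share, completed data | Share, true values, same labels | Ratio |
|---|---|---|---|
| 0% | 8.2% | 8.2% | 1 |
| 20% | 12.1% | 6.5% | 1.9 |
| 30% | 15.4% | 5.8% | 2.7 |
| 50% | 26.2% | 4.2% | 6.2 |

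With correlation 0.3 between variables, the share goes from about 28% with full data to 32% at 20% missing and 45% at 50% missing. The ratios to the true-value share at 20, 30 and 50% missing are about 1.2, 1.4 and 1.9.

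**Simulation 2.** This is closer to learning the model from complete data. Clusters are fitted to complete rows only, with 10 variables, k = 4 and correlation 0. The full-data share is 0.186.

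| Overall missing | Cluster mean | Random draw within cluster | Draw ignoring clusters | Rank-2 subspace |
|---|---|---|---|---|
| 10% | 0.210 | 0.200 | 0.185 | 0.206 |
| 21% | 0.246 | 0.216 | 0.187 | 0.233 |
| 35% | 0.312 | 0.242 | 0.194 | 0.288 |
| 40% | 0.350 | 0.254 | 0.198 | not run |

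With correlation 0.3 the full-data share is 0.343. Cluster-mean filling raises it to 0.371–0.496, and draws within clusters to 0.354–0.384.

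**Homogeneity in frailty itself** (simulation 2, correlation 0). If the frailty score is one of the partly imputed variables, the clusters explain 0.18 of its variance with full data and 0.32 at 35% missing. Among those whose score was imputed, they explain only 0.03 of the true score. If frailty is an unrelated, fully observed score outside the imputation, the explained share stays near 0.01 at every missing rate.

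**The case against.** Several stronger readings are tempting, and the documents do not support them.

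- A reader might infer that the plan selects clusters on tightness in feature space and so always rewards missing data. The stated criterion is homogeneity in frailty. Inflation there requires a frailty measure that is partly imputed or built from imputed variables.
- A reader might infer from the Fried exclusion that no outside measure exists. Section 2.4 points to hard and proxy outcomes. Hard outcomes come largely from the follow-up questionnaire (section 3.3), and section 5.2.2 plans survival models against them. These checks are real, but section 5.4.1 does not tie the clusters to them.
- A reader might infer that every missing value is set to a cluster centre. The text says only that prediction is based on clustering, which also fits random draws, and those inflate less. That the search runs on completed data is likewise inferred from sentence order.
- A reader might infer that observed readings will be overwritten as noise. The wording also fits ordinary smoothing of sensor signals.
- A reader might quote the independent-variable ratios of about 2 to 6 as the expected size. That is close to a worst case: device variables such as steps, walking time and posture are plainly related, and part of the ratio comes from the fall in the true-value share. Against the no-missing share, the same run gives 12.1/8.2 = 1.5 to 26.2/8.2 = 3.2.

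What stands after this is the mechanism. It appears with cluster means, with draws within clusters and with subspace filling, and the written plan contains nothing to detect it.

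**Conclusion.** The concern holds in conditional form. Section 5.4.1 itself pairs cluster-based imputation with a search for homogeneous clusters, so this is not a detail merely left to an analysis plan. If the search uses completed data, part of the homogeneity is produced by the imputation, even with data missing completely at random. The effect is largest with deterministic filling. It reaches homogeneity in frailty only when the frailty measure is itself partly imputed or built from imputed variables.

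The size is not known from the protocol. With moderately correlated variables, 20 to 50% missing and cluster-mean filling, an overstatement of about 1.2 to 1.9 times is a reasonable illustration. The documents do not show that the eventual categories will be artefacts. They show that the plan as written could not tell. The change should be made, and it affects the analysis only.

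**What to change.** Amend section 5.4.1 so that the same clustering is not used both to impute and to define frailty categories.

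1. Either impute from a model that carries no cluster labels but keeps the relations between variables (multiple imputation is one option), or cluster with a method that handles missing cells directly. Crude draws that ignore those relations are no remedy: with correlation 0.3 they took the share below its full-data value (0.26 to 0.31 against 0.34).
2. Derive the rules from observed values.
3. Judge homogeneity in frailty on held-out participants, or on a fully observed outcome kept out of the imputation, such as the hard outcomes where follow-up is complete. Do not rely on observed cells of the same participants alone.
4. If imputation is repeated, report whether the clusters recur across the imputed data sets.
5. State what handling of measurement noise means, and whether any recorded value is replaced.

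The cost is more computing and a rewritten imputation paragraph, with no new data or visits. Clusters will look less tight, and some may not survive.

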5.4.2.1 Ranking the significance of parameters

It is important to investigate the relevance of the data that we include in our parameter dataset, with the values provided by our model. As soon as the model has been established,

it will be assessed in regards to its ability to describe the data that we have. It is important to evaluate and fine tune the significance and contribution of each variable in the model.

To choose the statistically significant variables in a model, we will perform validation tests. These validations will help us investigate what variables do not contribute to the model, and therefore can be removed without loss of information. To investigate the adequacy of our model to describe transitions in frailty, a repertoire of sampling, distribution and statistical functions will be used. To rank the importance of the features or parameters we plan to use the ReliefF algorithm (86, 87). The ReliefF algorithm, which can operate on both discrete and continuous class data, evaluates the worth of an attribute by repeatedly sampling an instance and considering the value of the given attribute for the nearest instance of the same and different class.

For model selection, criteria such as the Bayesian information criterion (BIC) or the Akaike information criterion (AIC), will be used.

5.4.2.2 eFI exploitation

Linking eFI to our dataset will help us exploit the large sample size of the eFI database, which numbers more than 900k+ health electronic records. The eFI uses a 'cumulative deficit' model, which measures frailty on the basis of the accumulation of a range of deficits, which can be clinical signs (e.g. tremor), symptoms (e.g. vision problems), diseases, disabilities and abnormal test values. In total, the eFI is made up of 36 deficits comprising around 2,000 subparameters. The score is strongly predictive of adverse outcomes and has been validated in large international studies. We plan to link and associate a subset of our parameters to the eFI parameters at a higher level of abstraction at this stage so that we will be able to evaluate our population using their scoring system. This way, we will be able to strengthen the statistic viability of our study, whilst at the same time being able to assess the added value of the FrailSafe system to our participants.

5.4.2.3 Linking hard outcomes to parameters being measured

Due to the limited number of participants, the tight timeframe of the project and the frequency of occurrence of hard outcomes that can be used as ground truth for our models, we propose the use of significant clinical outcomes, or proxy outcomes, that we are confident that we will be able to measure and to use in the data analysis part of the project to draw solid conclusions. The proxy outcomes could also be considered as a diagnostic, early detection marker of a declining condition that may lead to a hard outcome. In addition to proxy outcomes we measure changes in numerous clinical measurements that comprise the CIFI, continuous quantitative technical measurements via the Frailsafe system that comprise the TFI as well as a combination of both. Through the intensive data analysis (that will include the use of probabilistic models such as Bayesian Networks) we will exploit as

much as possible the small number of hard outcomes and link them to proxy outcomes, the significant clinical outcomes and the more quantitative measures obtained by FrailSafe system to better understand frailty and its relation to comorbidities. In addition, by keeping a concise, short, practical yet informative track of the change (Δ) in proxy outcomes we will be able via coaching and interventions to postpone the inevitable occurrence of a hard outcome, thus improving prognosis and quality of life.

5.4.3 Detecting causality associations among various parameters

We intend to employ Bayesian Networks in order to inference causal relationships among different biosignals and other measurements/assessments of the older people. A BN is a probabilistic graphical model that represents a set of parameters and their probabilistic dependencies (88). In this model, nodes represent parameters of interest, e.g. observations such as high blood pressure, certain manifestation or not of frailty, presence of absence of comorbidities, drugs that have or have not been used, presence or absence of certain symptoms, while arcs encode the conditional dependencies among the variables. Because BNs are complete models for the parameters and their relationships, we will use them to answer probabilistic queries about them. A BN can be either specified by an expert and then used to perform inference, or it can be learned from data (89,90). We plan to use a combined approach and use expert knowledge when possible. To discover causal associations among temporal patterns we propose to use a variation of BNs called dynamic belief networks (DBNs) (91-93). DBNs are temporal models that permit inference across time.

Moreover, we plan to perform causal association studies to the parameters that we investigate in an effort to eliminate duplicate observations, overlaping observations and to achieve a more efficient association of each parameter to the domains under study (e.g. medical, technical, psychological etc).

6. Ethics and Safety

All throughout the study's methodology special care is taken for ethical and safety issues.

The very first step of each participant's recruitment concerns the clear information by both the information letter and the personal interaction with an authorised member of the study. Time is given for answering to questions that may emerge. In the information letter is provided description of the study's procedures, goals, possible benefits and inconveniences, hazard analysis as well as the declaration that the individual can drop out of the study at any time if (s)he wishes it.

In general, the present study does not contain high risk interventions. The installation and use of the FrailSafe system has a monitoring role and potential interventional interactions between the FrailSafe system and the participant are expected to be of no negative effect. Some mechanical hazards (i.e. risk of fall) that may underlie during certain procedures, especially the mobility testing and the virtual or augmented reality experiences when they are applied in a standing position, will be obviated by the attentive presence of a member of the study near the participant.

Material used in the study, essentially the FrailSafe system devices, receive calibration and technical service in the recommended intervals in order to avoid dysfunctions that may carry unforeseen consequences. Special care is given in the respect of the rules of hygiene, especially regarding devices in direct contact with a person's body (WWBS, scale for bioelectrical impedance AR glasses, tensionmeter). Alcoholic solutions are employed for the cleaning of all the instruments before use from the next participant, or equivalent cleaning instructions will be followed.

The WWBS devices are constructed in such a way so as to be washable in the washing machine after the disconnection of certain electronic parts. Moreover, materials and fabrics are also investigated considering functional and fashion aspects but also fully compatibility with body, preferring hypoallergenic and antibacterial materials, to guarantee a safe and prolonged use of the garment. This aspects as well as simplicity of use and easiness to don and doff the system are fundamental for a positive psychological impact on the patient, resulting in higher acceptability and usability of the overall platform. Of course special care to acceptability and tolerance issues will be given regarding all FrailSafe system devices.

The acceptability of the devices to be used by the participant also depends on the fact that no major limitations in the daily activities is expected to rise due to the study. Participants are supposed to continue their personal routine normally and be monitored in their natural environment and activities' framework. Logical adjustments of the study's time programming could be discussed according to the personal program, preferences and participant's availability.

Furthermore, the nature of the study requires the collection, processing, transfer and analysis of a large amount of data. In all these stages, confidentiality and personal data protection will be reassured by an anonymization procedure. Each participant is traced by his/her ID number and only this, and no identifiable personal data, is exposed to large scale data exchange. There will be nowhere a depiction of the participants' faces, no exact date of birth (only the year of birth will be recorded) and in the electronic and paper CRFs only the first two letters of the subject's first and last name will appear, along of course with the ID number. Only specific investigators from each centre will have access to the participants' coordinates' lists and the corresponding files will be kept under circumstances of security. The data collection and persistence will comply with the data protection guidelines reported in deliverable "D9.9: Ethics, Safety and mHealth Barriers" (Section 6) with the aim of, at same time, keeping the maximum level of security and privacy of the data and allowing the

successful performance of the clinical research and of the other tasks of the project. Moreover, data are obtained in accordance to the local ethics requirements. Any personal information regarding the participants is treated as sensitive personal data (as defined in deliverable D9.9) and kept strictly private. Recorded data are anonymized with no personal identifiers and no means to link these to personal identifiers – hence falling outside the scope of legislation concerning personal data.

It is important to notify that during the experimental period of the study the proposed devices are instruments still evolving with sensitivity properties which have not yet been tested. Thus, the FrailSafe system will not aim at taking in charge emergent situations or adverse event which may coincide during the enrolment period, although no undesirable effects are expected to occur due to the FrailSafe system instauration.

However, emergencies, such as a fall or serious arrhythmias, may randomly occur during the study; these emergencies, more specifically, may occur either during the use of the under development FrailSafe system or during the use of the prototype FrailSafe during the evaluation phase.

It is stressed that the FrailSafe team will not be aware of any emergency in real time. During the whole period of the study the analysis of data will be off-line, as a 24hours emergency response service was neither planned nor budgeted. However, the system will include a real time analysis and response, developed in the lab using off-line participants' data; the real time analysis is a feature which will be included, after the end of the project, in the market product.

Except of emergencies, incidental finding may also occur either during the clinical evaluation and follow up or during the use of the FrailSafe system.

a. Incidental findings during clinical evaluation and follow up:

If the researcher during the clinical evaluation finds out medical issues, which according to his/her professional judgment, need to be reported, the guidelines of the protocol on incidental clinical findings will be followed. This protocol will be devised locally in each clinical center, will be put to the attention of the local Ethics Committee, and briefly described in the participant's information sheet. The protocol will state that in case of such events the participant will be informed, and his permission will be sought for his medical practitioner and/or his family and/or carer to be notified.

b. Incidental findings during FrailSafe evaluation

These events are expected to be infrequent, as continuous data will be analysed in batches, and not individually. However, single cases may be needed to be considered individually, and so, such events may still occur. It should be also considered that continuous data will be analyzed off-line at a later stage, definitely after participants having completed the continuous recordings; 5-days recordings for most of the participants and 2-month recordings in the subgroup of the evaluation stage. Thus, incidental events are expected to be historical, though still need to be reported. A similar procedure as in incidental findings during clinical evaluation will be followed.

A protocol on incidental findings during FrailSafe evaluation will be set up locally in each clinical center, will be put to the attention of the local Ethics Committee, and briefly described in the participant's information sheet. The protocol will state that in case of such an event the participant will be informed, and his permission will be sought for his medical practitioner and/or his family and/or carer to be notified.

